**Investigational drug, drug ordering and accountability, storage conditions, and technical problems**

The investigational drug is zoledronic acid 5 mg/100mL - a bisphosphonate for intravenous infusion. Participants will be given a full dose of 5 mg, which is the standard dose for treatment of osteoporosis as an infusion over 30 minutes. The drug will be supplied by the hospital pharmacy and delivered directly to our research facility at Aarhus University Hospital, where we will perform our standard regimen of quality control. The drug will be stored in a locked closet at room temperature. In case of technical problems with the drug it will be replaced, and the drug returned to the pharmacy. Technical problems include discoloration, particles or contamination, leakage, or cracks. The investigator is accountable for the drug. Drugs will be administered according to the randomization. As part of the standard treatment of osteoporosis a daily intake of 1000mg calcium and 38ug vitamin D will be secured by supplementation.

**Duration of study**

Included patients will be part of the study for up to 30 months. The primary endpoints will be investigated 12 months after infusion of zoledronic acid. The participants will receive a letter from the investigator after the termination of the study with information about the study results.

Study plan

Group 1: 6-month group	Baseline	M1	M3	M6	M12	M16	M20	M24
Informed consent	X							
Medical history	X							
Physical examination	X							
Bone markers	X	X	X	X	X	X	X	X
Biochemistry	X				X			
HR-pQCT	X				X			
DXA	X			X	X			X
Zoledronic acid treatment	X							
Fracture history	X				X			X
Telephone call						X	X	

Group 2: 9-month group	Baseline	M1+2 	M3	M4	M6	M9	M15	M19	M23	M27
Informed consent	X									
Medical history	X									
Physical examination	X									
Bone markers	X	X	X	X	X	X	X	X	X	X
Biochemistry	X						X			
HR-pQCT	X						X			
DXA	X		X			X	X			X
Zoledronic acid treatment			X							
Fracture history	X						X			X
Telephone call								X	X	

Group 3: Observation group	Baseline	M1-5 	M3	Mx 	Mx+1	Mx+2	Mx+6	Mx+12	Mx+16	Mx+20	Mx+24
Informed consent	X										
Medical history	X										
Physical examination	X										
Bone markers	X	X		X	X	X	X	X	X	X	X
Biochemistry	X							X			
HR-pQCT	X							X			
DXA	X		X	X			X	X			X
Zoledronic acid treatment				X							

Fracture history	X							X			X
Telephone call									X	X	

 M1 + M2: Month 1 and month 2 after baseline.

 M1 - M5: Month 1 to month 5 after baseline.

 Mx: months after baseline, depends on when the specified levels of p-CTX or BMD loss are achieved

### Investigations

*Bone turnover markers:* Biochemical markers of bone turnover are s-bone alkaline phosphatase (s-BSAP), p-osteocalcin, p-PINP and p-CTX. The samples will be collected in peripheral blood samples in the morning (7:30–10:45 a.m.) after a minimum of eight hours of fasting, then centrifuged at 400 rpm at five degrees Celsius for ten minutes and stored at -80 degrees Celsius. P-CTX, p-osteocalcin and p-PINP will be analyzed on EDTA plasma using ELISA (Cobas 6000 immunoassay analyser, Roche Diagnostics GmbH) and BASP on serum using immunochemical reaction (ISYS). The samples will be analysed in a batch at the Department of Biochemistry, Aarhus University Hospital to reduce the analytical variation. The precision is  $\pm 7.4\%$  at 32  $\mu\text{g/l}$  (95% CI),  $\pm 10\%$  at 0.30  $\mu\text{g/l}$ ,  $\pm 6\%$  at 18  $\mu\text{g/l}$  and  $\pm 20\%$  at 44.4  $\mu\text{g/l}$  for p-PINP, p-CTX, p-osteocalcin and s-BSAP, respectively. If the results of any of the blood samples are below or above the detection range, we will use the lowest or highest detectable value, respectively. The BTMs will be measured at every clinical visit. If the specified p-CTX level is reached before month three (nine-months group) or month six (observation group) zoledronic acid will be administered.

*Biochemistry:* Markers of diseases affecting bone metabolism (calcium, phosphate, magnesium, 25-OH-vitamin D, PTH, creatinine, alkaline phosphatase, TSH). The samples will be analyzed at the Department of Biochemistry, Aarhus University Hospital.

*Bone mass:* Areal bone mineral density (aBMD) ( $\text{g/cm}^2$ ) of the lumbar spine (L1-L4) and hip (left) will be measured using a Hologic Discovery scanner (Hologic, Inc., Waltham, MA, USA). The right hip was scanned in case of prosthesis at the left hip. All participants were examined on the same DXA scanner throughout the trial. Incident vertebral fractures will be investigated using the vertebral fracture assessment (VFA) tool on the Hologic Discovery scanner. Lumbar spine trabecular bone score (TBS) will be measured using the TBS iNsight software, version 2.1.0.0 (Medimaps, Merignac, France).

*Bone quality:* Bone microarchitecture and estimated bone strength will be assessed by a high-resolution peripheral quantitative computed tomography (HR-pQCT) scan of the distal radius and tibia.

*Treatment:* An intravenous infusion of 5 mg zoledronic acid will be administered at study day 0 (6-months group), at month three (9-months group), or depending on increase in p-CTX, decrease in BMD, or the occurrence of an osteoporotic clinical vertebral or hip fracture, but no later than at month 6 (observation group). The patients will be monitored with DXA 6, 12 and 24 months after the infusion of zoledronic acid. Zoledronic acid will be re-administered if BMD has decreased more than 5% at the lumbar spine, total hip or femoral neck. If p-CTX increases above 1.26  $\mu\text{g/l}$  during the 2nd year a second infusion of zoledronic acid will be administered.

*Fracture history:* Participants will be questioned about incident fractures at months 12, 15, or x+12 and again at months 24, 27, or x+24. Information will be confirmed using discharge notes from hospitals.

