## **Study population and methods**

### **Design**

A randomized open label, interventional study in 60 patients investigating if treatment with zoledronic acid prevents bone loss after denosumab treatment when administrated six (6-month group, n=20) or nine months (n=20, 9-month

group) after last injection of denosumab or when bone turnover is increased (n=20, observation group). Forty patients will be allocated to the two intervention groups and 20 patients will be followed without treatment for up to 12 months after the last denosumab treatment. The patients in the observation group and the nine months group will be monitored monthly and if p-carboxy-terminal collagen crosslinks (p-CTX) increases above 1.26µg/l (50% above the normal range for postmenopausal women and elderly men) infusion of zoledronic acid will be administered. Furthermore, a DXA scan (lumbar spine and hip sites) will be performed after three months in the observation group. If BMD has decreased more than 5% at the lumbar spine or total hip, infusion of zoledronic acid will be administered. Finally, if a patient in the 9 months group or the in the observation group suffers an osteoporotic clinical vertebral or hip fracture, infusion of zoledronic acid will be administered.

The patients will be given a single infusion of zoledronic acid as the increase in bone turnover seen after stopping denosumab seems most prominent in the first year [12]. The patients will be monitored with DXA 6, 12 and 24 months after the infusion of zoledronic acid. Zoledronic acid will be re-administered if BMD has decreased more than 5% at the lumbar spine, total hip or femoral neck.

If p-CTX increases above 1.26 µg/l during the 2nd year a second infusion of zoledronic acid will be administered.

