#### **Co-primary endpoint**

- Change in lumbar spine BMD from baseline to 6 months after the zoledronic acid infusion.
- The proportion of patients who fails to maintain BMD (total hip, femoral neck and spine). Failure is defined as  $\geq 3$  % BMD loss at the lumbar spine or  $\geq 5$  % BMD loss at the femoral neck or total hip.

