#### **Secondary endpoints**

- Changes in total hip, femoral neck and lumbar spine BMD from baseline to one year after the zoledronic acid infusion.
- Changes in total hip, femoral neck and lumbar spine BMD from baseline to two years after the zoledronic acid infusion.
- Changes in trabecular bone volume fraction (bone volume/tissue volume, BV/TV) and cortical porosity measured by high-resolution peripheral quantitative computed tomography (HR-pQCT) scan at the radius and tibia from baseline to one year after the zoledronic acid infusion.
- Changes in p-CTX and p-procollagen type I N-terminal propeptide (p-PINP) from baseline to six months after the zoledronic acid infusion.
- Changes in p-CTX and p-PINP from baseline to 12 months after the zoledronic acid infusion.
- Morphometric vertebral fractures assessed by vertebral fracture assessment (VFA) one and two years after the zoledronic acid infusion.

---

 Electrochemiluminescence immunoassay (ECLIA) will be used.

 Reference range: Women 30-50 years: 0,04 - 0,59 µg/l. Women > 50 years: 0.03-0.83 µg/l. Men 30-50 years: 0,09 - 0,63 µg/l. Men 50-70 years: 0.04-0.84 µg/l. Men > 70 years: 0,08 – 1,05 µg/l.

 ECLIA will be used.

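### The plan does not say how patients re-infused for BMD loss are scored, so failures at 6 months can count as maintained at 12 months

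*Combined protocol and SAP*

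**What the plan says.** All places are in the combined protocol and SAP.

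- **Treatment.** Design states "The patients will be given a single infusion of zoledronic acid". Investigations (Treatment) adds "The patients will be monitored with DXA 6, 12 and 24 months after the infusion of zoledronic acid" and then "Zoledronic acid will be re-administered if BMD has decreased more than 5% at the lumbar spine, total hip or femoral neck". If p-CTX exceeds 1.26 µg/l in the second year, "a second infusion of zoledronic acid will be administered".
- **Co-primary endpoints.** The first is "Change in lumbar spine BMD from baseline to 6 months after the zoledronic acid infusion". The second is a failure proportion. Failure means a loss of at least 3% at the lumbar spine, or at least 5% at the femoral neck or total hip. That section gives no time for it.
- **Timing.** Duration of study says "The primary endpoints will be investigated 12 months after infusion of zoledronic acid", which conflicts with the 6 months given for the first co-primary.
- **Secondary endpoints.** These include BMD, HR-pQCT and bone markers at one year, and "Changes in total hip, femoral neck and lumbar spine BMD from baseline to two years after the zoledronic acid infusion".
- **Analysis.** Statistical analysis and power calculation plans paired and one-sample t-tests on one-year BMD change (the latter against a published discontinuation study), a chi-square test on failure, and mixed models between groups. It ends with a per-protocol analysis whose population is not defined. Re-infusion is not mentioned.

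**The concern.** The outcome itself triggers the second infusion. If loss is measured from the same baseline scan in both places, a loss above 5% at any of the three sites always meets the failure definition. So the patients re-infused after the 6-month scan are the clearest failures, and they are treated again before the 12-month scan at which the primary endpoints are said to be read.

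The failure definition looks only at the BMD value, so a re-infused patient who regains enough bone becomes a success. The error runs towards the conclusion that BMD is maintained. It is larger in whichever group loses more bone, so it also narrows real differences between the timing groups.

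The same gap reaches:

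- the one-year BMD change, including its comparison with the published discontinuation study;
- the 12-month HR-pQCT and bone markers;
- all two-year outcomes, where re-infusions triggered at 12 months or by p-CTX are added.

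**Working it through.** **Order of events.** 6-month scan, then re-infusion if the loss exceeds 5%, then the 12-month scan. The first co-primary is read at the 6-month scan, before any BMD-triggered re-infusion, so it is not affected. The p-CTX trigger applies in the second year (read here as the second year after infusion), so it cannot affect the 6- or 12-month scans.

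**Inputs from the plan.** SD 3%; 20 patients per group; re-infusion at a loss above 5%; spine failure at a loss of 3% or more; between-group difference of interest 3 points.

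**The plan's own sample sizes, which use the same SD.**
- Paired, 2.5% change, 90% power, two-sided 5%: (3 × (1.960 + 1.282) / 2.5)² = 15.1 by the normal approximation, and 17.2 by the t distribution. Rounded up, the latter gives the plan's 18.
- Two-sample, 3% difference, 80% power: 2 × (3 × (1.960 + 0.842) / 3)² = 15.7, so 16 per group as stated. The exact t calculation gives 16.7, so 17.

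Both reproduce within rounding.

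**Assumptions not in the plan.** The 3% SD is applied to the 6-month change. The change is Normal with mean μ between 0 and -3%. Patients who are not re-infused stay where they are between 6 and 12 months. Re-infused patients regain g = 2, 3 or 4 points. Only the spine is used, because no hip SD is given; hip sites would add triggers.

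**Formulas.**
- Re-infused: P(X < -5) = Φ((-5 - μ)/3).
- Rescored as maintained: P(-(3 + g) < X < -5), because the patient must end above -3%.
- Shift in the one-year mean: P(X < -5) × g.

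| μ | Re-infused | Of 20 | Rescored of 20, g = 2 | g = 3 | g = 4 | Mean shift, g = 2 to 4 |
|---|---|---|---|---|---|---|
| 0 | 4.8% | 1.0 | 0 | 0.5 | 0.8 | 0.10 to 0.19 |
| -1% | 9.1% | 1.8 | 0 | 0.9 | 1.4 | 0.18 to 0.36 |
| -2% | 15.9% | 3.2 | 0 | 1.3 | 2.2 | 0.32 to 0.63 |
| -3% | 25.2% | 5.0 | 0 | 1.9 | 3.2 | 0.50 to 1.01 |

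With g = 2, a patient below -5% is still below -3%, so nobody is rescored.

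**If re-infused patients are dropped instead.** At μ = -3%, the spine failure rate goes from 50.0% to (0.500 - 0.252)/(1 - 0.252) = 33.1%. At μ = 0 it goes from 15.9% to 11.6%.

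**Between two groups with means 0 and -3%, 20 per group.** In simulation of 40,000 trials, power of the pairwise chi-square test is 67% if failures stay failures. It is 67% with g = 2 and 52% with g = 3. As an outer bound, if every re-infused patient recovers, failure is 11.1% against 24.8% instead of 15.9% against 50.0%, and power by the normal approximation falls from 64% to 20%. For mean BMD change, the 3-point difference shrinks to 2.6 (g = 2) or 2.4 (g = 3), and t-test power falls from 87% to 86% or 84%.

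**The case against.** The strongest reply is that the plan is silent rather than wrong. A reader might infer that re-infused patients are to be analysed as though they had one infusion. No section says that. It is what happens by default if observed values are used, and exclusion under the undefined per-protocol analysis is equally open. This is correct, but it does not remove the problem: both routes lower the failure rate.

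Second, re-infusion is part of the protocol, so analysing all observed data validly estimates the effect of the whole strategy. That stands for BMD change, and it is why the all-data mixed model should stay. It does not justify calling a patient maintained on a single infusion after that patient has failed and been treated again.

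Third, read at 6 months, or as failure at any scan, the failure endpoint has no such problem. True, but the plan adopts neither reading, and the only time it gives for the primary endpoints collectively is 12 months.

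Fourth, the effect on mean BMD change is modest, and the plan calls its between-group analyses exploratory. Both points stand. The failure proportion is more sensitive, and it is a co-primary endpoint.

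Three further inferences should be resisted:

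- Not every re-infused patient would be rescored. At the spine that needs a regain of more than 2 points, and more for larger losses.
- The two-year changes are not compared with published losses. The two years in that sentence of the statistical section describe earlier denosumab treatment, and the comparison is of one-year change.
- A second infusion triggered by p-CTX does not show BMD failure.

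**Conclusion.** The concern holds as a gap with a predictable direction. With failure scored on the observed 12-month scan, patients who had already met the definition can be recorded as maintained. Excluding them under an undefined per-protocol set pushes the same way.

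On the spine criterion alone, about 1 to 5 of 20 per group would be re-infused. Between 0 and about 3.2 of those would be rescored, and the one-year mean would rise by about 0.1 to 1.0 points. The plan treats a fall smaller than 2.5% as BMD maintained. In the most affected case shown, a true mean of -3% would read as about -3 + 1.0 = -2.0% and so fall inside that limit.

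These sizes rest on the assumed mean change, on the 3% SD holding at 6 months, and on an assumed regain that the documents do not give. They also require loss to be measured from the same baseline scan for the trigger and the endpoint; the reference scan for the trigger is not stated. A reader might infer that both co-primary endpoints are compromised. The documents do not support that, because the 6-month spine change is read before any BMD-triggered re-infusion.

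**What to change.** 1. Reconcile Co-primary endpoint with Duration of study, and set one time point for the failure endpoint.
2. Count a patient as a failure if the definition is met at any post-infusion scan up to that time. State that loss is measured from the same baseline scan; the rule then includes every patient re-infused for BMD loss. A second infusion triggered by p-CTX should not by itself count as a BMD failure.
3. Define the per-protocol set, state that re-infusion required by the protocol does not remove a patient from it, and report the number of re-infusions by group and trigger.
4. Keep the all-data mixed model for one- and two-year BMD. Add a pre-specified supplementary model with scans after a second infusion set to missing, labelled as the effect of a single infusion.

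The re-infusion rule stays as it is and no new data are needed. The cost is SAP wording, one extra model, and slightly less favourable failure proportions.

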## **Data management**

### **Source data identification and verification**

Source data will be entered into the patient file and/or the CRF. Most data will be found both in the patient file and the CRF, but some source data, for example body weight and height will be entered directly into the CRF. This will be specified in the source data file. The investigators, the monitor from the GCP-unit at Aalborg and Aarhus University will perform data verification.

### **Subject data protection**

Access to CRFs will be limited to investigators and other healthcare professionals involved in this study. Data from the patient files can be passed on to healthcare professionals at the hospital who are in charge of the treatment of the participants. Data may also be passed on to the monitor from the GCP-unit and inspectors from the Danish Health authorities. The patient files are electronic and kept on the hospital electronic patient file system. Any printouts of the patient files and the CRFs will be kept behind locked doors after working hours.

### **Data handling**

When data analyses is finalized, the data will be converted to an anonymous form using participation numbers only, and names and social security numbers will be removed.

### **Statistical analysis and power calculation**

Baseline characteristics of the three groups will be presented using descriptive analysis and compared using ANOVA and post-hoc unpaired t-tests if ANOVA demonstrates differences between the groups. Changes in bone mineral density one year after the zoledronic acid infusion within groups will be investigated using paired-sample t-tests and compared with the changes reported after stopping denosumab after two years [12] for the three groups combined and individually using one-sample t-test. The proportion of patients who fails to maintain BMD will be compared between groups using chi-sq test. Changes in bone mineral density, HRpQCT measures and markers of bone turnover will be compared between groups using mixed model analysis. Exploratory analyses will include multiple regression analyses aiming at identifying baseline factors or changes occurring at three or six months, which affect the change in BMD one year after the zoledronic acid infusion. Factors included in this analysis will be gender, age, years of treatment with denosumab, baseline BMD, baseline bone turnover markers, change in bone turnover markers three and six months after the zoledronic acid infusion.

Based on a previous study a 5% decrease in lumbar spine BMD can be expected during the first year after discontinuation with a 3% standard deviation [12]. The hypothesis is that treatment with zoledronic acid can decrease this bone loss. Eighteen patients will be needed to demonstrate a bone loss  $\geq 2.5$  % using a paired-sample t-test with a power of 90% and level of significance of 5%. If the decrease is less than that BMD is maintained and the hypothesis can be accepted. To account for dropouts n is increased to 20 in each group. As comparisons between the different treatment regiments suggested in this protocol never have been done before, we cannot estimate differences between groups. However, the least significant change in lumbar spine BMD using DXA is 3%. The SD of lumbar spine BMD in our facility is 3% [18]. To be able to demonstrate a difference in change in lumbar spine BMD between the three groups equal to the least significant change using independent samples t-test we need 16 patients in each group with a standard

deviation of 3%, power of 80% and significance level of 5%. Thus, the already planned 20 participants per group are sufficient to make meaningful exploratory analyses. New participants will be enrolled after four dropouts in total. Per-protocol analysis will be performed.

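### Separate paired t-tests for within-arm one-year BMD change drop patients without the one-year scan; one mixed model over the repeated DXA scans would keep them, for a modest gain

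*Combined protocol and SAP*

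**What the plan says.** All statements on analysis are in the protocol section on statistical analysis and power calculation.

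- Within arms: "Changes in bone mineral density one year after the zoledronic acid infusion within groups will be investigated using paired-sample t-tests". The same changes are then set against a published change after stopping denosumab, "for the three groups combined and individually using one-sample t-test".
- Between arms: "Changes in bone mineral density, HRpQCT measures and markers of bone turnover will be compared between groups using mixed model analysis". The model's time points, covariance structure and covariates are not given.
- Sample size: "Eighteen patients will be needed to demonstrate a bone loss $\geq 2.5$ % using a paired-sample t-test", from an expected "5% decrease in lumbar spine BMD can be expected during the first year after discontinuation with a 3% standard deviation", at 90% power and 5% significance. The number per arm is raised from 18 to 20 for dropouts.
- Reading of the result: "If the decrease is less than that BMD is maintained and the hypothesis can be accepted".
- Analysis set: per-protocol, with new participants enrolled after four dropouts in total. No method for missing BMD values is stated.

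Under Investigations, the scan schedule is: "The patients will be monitored with DXA 6, 12 and 24 months after the infusion of zoledronic acid".

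The endpoint lists make the 6-month lumbar spine change co-primary and the one-year BMD changes secondary. The section on duration of study instead places the primary endpoints at 12 months. These two statements need to be reconciled.

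**The concern.** Every arm is to receive zoledronic acid, so whether bone mass is maintained is judged largely from the change within each arm, in about 18 to 20 patients. For that estimate the plan names a method that uses two scans per patient and drops anyone who lacks the second, even when a 6-month scan exists.

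Two things are at stake. One is precision, since a dropped patient's 6-month value says something about the missing one-year value. The other is bias. If patients who lost more bone by 6 months are less likely to have the one-year scan, the completers look better than the arm as a whole. That error favours the conclusion that BMD is maintained. The within-arm and between-arm results could also rest on different patients.

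**Working it through.** **Inputs from the protocol.** SD of change 3%; loss of interest 2.5%; 18 patients per arm raised to 20; scans at 6, 12 and 24 months after infusion.

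**Assumptions, not in the documents.** Correlation ρ between the 6- and 12-month changes of 0.5 to 0.85; 2 of 20 one-year scans missing per arm (the plan's own 20 against 18), with the 6-month scan present; the missingness mechanism in step 5.

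**1. The plan's figure.** Exact noncentral-t power for a paired test with standardised effect 2.5/3, two-sided 5%: 89.7% at n = 17 and 91.5% at n = 18. The stated 18 reproduces.

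**2. Complete data, 20 per arm.** The unadjusted arm mean is the same under both methods. Only the degrees of freedom can differ, and only if one variance is pooled over the arms.
- Separate: t(0.975, 19) × 3/√20 = 2.093 × 0.671 = 1.40 points; power for 2.5% is 94.2%.
- Pooled: t(0.975, 57) × 3/√20 = 2.002 × 0.671 = 1.34 points; power 95.6%.

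**3. Is pooling safe?** In a simulation with 20 per arm and assumed SDs of 2.5, 2.5 and 4, the pooled variance gives a within-arm type I error of about 13% in the SD 4 arm and about 1.7% in the others. Separate t-tests hold 5%. Infusion time varies in the observation arm, so equal variances should not be presumed.

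**4. Two of 20 one-year scans missing.**
- Paired test, 18 completers: t(0.975, 17) × 3/√18 = 2.110 × 0.707 = 1.49 points.
- Using the 6-month scan: variance = 9 × [(1 − ρ²)/18 + ρ²/20].
  - ρ = 0.5: 9 × (0.75/18 + 0.25/20) = 0.4875; SE 0.698; effective n = 9/0.4875 = 18.5.
  - ρ = 0.85: 9 × (0.2775/18 + 0.7225/20) = 0.4639; SE 0.681; effective n = 9/0.4639 = 19.4.
- Arm-specific variance (17 df): 2.110 × 0.698 = 1.47 and 2.110 × 0.681 = 1.44. Estimating the regression on the 6-month change multiplies the first variance term by about 1 + (2/20)/(18 − 3) = 1.0067. At ρ = 0.5 the SE becomes 0.700 and the half-width 1.48. The range is therefore about 1.44 to 1.48, or 1% to 4% narrower than 1.49.
- Common variance (51 df): 2.008 × 0.698 = 1.40 and 2.008 × 0.681 = 1.37, valid only if the arms share one variance.

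**5. Missingness that depends on the 6-month change.** Simulated with 20 patients in an arm, SD 2.5% or 3% at 6 months and 3% at 12 months, and a logistic chance of a missing one-year scan that rises with 6-month loss (slope 0.3 or 0.5 per point), set to about 10% missing. Completers understate the mean loss by roughly 0.1 to 0.3 points. The estimate that uses the 6-month scan is within about 0.02 of the truth. Another illustrative mechanism (SD 3%, ρ = 0.7, logistic intercept −2, slope 0.5) gave about 0.5 against 0.02. The size depends on the assumptions. The direction follows whenever larger early loss makes a missing scan likelier and the two changes are positively correlated.

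**The case against.** The strongest reply is that nothing here is wrong. A paired t-test is a correct test of a within-arm change, matches the sample-size calculation and makes no assumption across arms. With 18 completers it still has 91.5% power against the planned 90%. This stands, and it is why the point is a cheap improvement only.

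The bias figure rests on an invented mechanism. Nothing in the documents shows that missing the one-year scan depends on the 6-month result. That also stands. A bias of 0.1 to 0.3 points is 4% to 12% of the 2.5% threshold (0.1/2.5 to 0.3/2.5).

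A mixed model recovers nobody whom the analysis set excludes. The plan is per-protocol, replaces dropouts, and in a footnote under Randomization reuses their codes. A patient lost before the 6-month scan adds no post-infusion value under either method. This stands, and the fix must address it.

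Stronger readings are tempting but unsupported:
- A reader might infer that a model over all arms and all scans is already planned. The protocol says only that changes are compared between groups by mixed model, so the model has still to be specified.
- A reader might equate the gain with 10% to 17% more patients per arm. That needs a common variance. With arm-specific variances, effective n rises only from 18 to about 18.5 to 19.4.
- A reader might treat the one-year paired tests as carrying the trial's main answer. The one-year change is listed as secondary, the co-primary lumbar spine change is at 6 months, and the one-sample tests against the published change address the same question. The duration section and the power text do point towards one year, but that is a conflict to reconcile and does not settle the matter.

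**Conclusion.** The point holds as a modest improvement. The paired tests are valid with complete data, and there the mixed model with arm-specific variances offers essentially nothing. The benefit appears when one-year scans are missing: a half-width of about 1.44 to 1.48 instead of 1.49 points with 2 of 20 missing (1.37 to 1.40 only if variances are equal across arms). There is also protection against a bias of roughly 0.1 to 0.3 points if missingness follows the 6-month change. Of the two, the protection against bias is the better reason to change, because that bias would favour concluding that BMD is maintained. These figures rest on the protocol's SD of 3%, the assumed correlation and missingness, and incomplete patients staying in the analysis.

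**What to change.** In the section on statistical analysis and power calculation, replace the within-group paired tests as the main within-arm analysis. Estimate arm-specific BMD changes with 95% confidence intervals at 6, 12 and 24 months after infusion from one mixed model with terms for arm, visit, and arm by visit. Use an unstructured covariance with arm-specific variances by default. Include all randomised patients with at least one post-infusion scan, not only per-protocol completers, and state that replaced dropouts keep their data in the analysis. Retain the paired t-test as a sensitivity analysis. Reporting all three time points serves whichever endpoint timing is confirmed.

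The cost is a few sentences and no new patients or scans. The downsides are slightly more modelling and reliance on data being missing at random. The 24-month values may follow a second infusion, which the plan allows, so it should say how those values are treated.
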